### **Inclusion criteria**

1. The patient has adenomas larger than 20 mm in size

2. The patient is willing to accept the treatment and follow-up program for1 year.

3. The patient is capable to understand and follow the instructions. The patient gives written informed consent.

Patients meeting the following exclusion criteria will be excluded from the study:

- 1. Patients allocated to "high-risk" group because of many small polyps (>4).
- 2. Mental illnesses or suspected significant compliance challenges.
- 3. Pregnancy.
- 4. Known allergy to carrots.

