# **Project description**

### WP1. Px7 Clinical trial (Lead: OUH. Partners: KUH, UUH, UMU, DR, NF, OF)

# Task1.1 Cultivation and quality control of carrots and juice production(Lead: OUH. Partners: DR, NF, OF)

DR will ensure timely production of the necessary amounts of "Yellowstone" carrots. The carrots will subsequently be transported to OF and NF, for production of both the carrot and the placebo juice. The final products will be shipped to the included centers 4 times a year. Other preparatory activities will also be handled in this task.

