# Methodology

# Design of the intervention

The trial will be conducted as a double-blind controlled, randomized study. Patients, who, at colonoscopy, had high-risk adenomas, are randomized in 2 arms. One arm will receive 100 ml of carrot juice with a high concentration of falcarinol and falcarindiol daily for 1 year and the other arm will receive 100 ml of placebo juice daily for 1 year until their follow up full colonoscopy. The placebo juice will be produced from commercially available artificial juice without Falcarinol or Falcarindiol. At the follow up colonoscopy, another standardized report will be fulfilled by the endoscoper, containing information about recurrence, the number of polyps, polyp size and risk stratification (no-, low-, medium, high risk polyps or cancer).

The compliance will be registered through diaries/calendars and patients will be followed through the entire period, regardless of their level of compliance. Patients with compliance drop-outs will be encouraged to reenter and complete with as high a compliance as possible.

Patients will be informed that they will receive a call after 1 month from each appointment, where their questions and concerns will be answered.

After the first colonoscopy, patients will be offered inclusion into the trial. If the resection of the high-risk polyp took place in the first colonoscopy, the patient will call the project nurse if he/she is interested in participating in the study and make an appointment for being enrolled in the project. If the resection will take place in a specialized unit where a second colonoscopy will be performed for the resection, then they will give their final answer at this appointment.

The patient will collect 8 liters of juice/placebo every 2 months at a visit at the clinic. At this visit, they will be interviewed for compliance, intake of additional carrots/carrot containing products and possible side effects. If the project nurse assesses the patient as non-compliant then he/she will be excluded from the study.

Each participant will have 6 visits and the 4 institutions will in total have 2400 visits, which is approximately 600 visits in two years at each institution. Visits can be organized in weekly group sessions. Compliance diaries and questionnaires will be explained and collected according to written instructions.

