### Scenario 1 - Resection at first visit:

Finding and removing high-risk polyp at the current colonoscopy

After performing the colonoscopy, the endoscopist will consider the inclusion and exclusion criteria and if the patient is eligible he/she will be given an oral information about the study (attachment 4 b). All information will be given along with information about the finding from the colonoscopy according to national guidelines in privacy by the endoscopist or the specialized nurse (in a private room with close d doors to ensure patient confidentiality). The patient is informed that he/she has the right to have a person of his own choice to participate. If the person is not there at the moment, the patient can come accompanied after the 48 hour time to think, to a talk at the scheduled location – the information will also be given accordingly to confidentiality guidelines in a private room by an endoscopist or the specialized nurse. The patient will receive written information and informed consent to bring home and will be given at least 48 hours of consideration time before signing it. The patient will call the project nurse if he/she is interested in participating in the study and will not be contacted regarding the clinical study if he/she does not contact us.

If the patient agrees, he/she will come to the facility with informed consent signed and will be instructed by the project nurse and also receive a diary/calendar, questionnaire and 8 liters of juice for 2 months treatment.

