# Risks disadvantages and side effects.

The risks are considered low. Few patients will have a control colonoscopy earlier by 3 months (as was the standard procedure until May 2023). The clinical guidelines for a follow up colonoscopy has been after 1 year in Denmark until May 2023. As European, British and American as well as Swedish guidelines offer a 1-3 year follow up there will be no risk for the patient to have the follow up after 1 year.

Carrot juice are considered health promoting for several reasons, and any toxic dose cannot be obtained with the amounts delivered. Discoloration of skin might be seen I cases who take higher doses than recommended. The placebo juice is produced by commercially available juice and taste additives (ginger). The calories contained in both products might theoretically give a low gain of body weight.

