### Information collected from patient files and questionnaires:

From the patient file: Quality and technical details of both colonoscopy, allergies, former colonoscopies and polypectomies and the pathology report on adenomas resected. Only data necessary to answer the described aims will be collected.

We will not need to give patient information to others to recruit patients. The patients will be invited to participate if they have a polyp bigger than 20 mm regardless of other information from the patient journal which we will not access at this timeline. Patient information will not be collected at the inclusion but will be accessed by research responsible and entered into a RedCap database after the patient will be already included in the project. Only project members have access to data and data will be destroyed after analysis. The project will be registered in the Data Protection Agency. The data protection law and regulations will be obeyed including the chapter V.

Data obtained in Sweden will be entered into the Danish RedCap database in OPEN directly after a data sharing agreement has been lawfully obtained between the sites. After the completion of the database all data will be pseudoananomized. Data will be destroyed after publication of the results from the 3-year colonoscopy, or – if scientifically useful, prolongation until the 5-year colonoscopy will be applied for.

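### The only allergy exclusion names carrots, although the placebo is described as other juice with ginger, and the file's allergy entry is read only after inclusion

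*Protocol*

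**What the plan says.** The Protocol, Inclusion criteria, lists four exclusions. The fourth, and the only one about allergy, is "Known allergy to carrots".

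The placebo is described in three places. Under Design of the intervention: "The placebo juice will be produced from commercially available artificial juice without Falcarinol or Falcarindiol". Under Risks disadvantages and side effects: "The placebo juice is produced by commercially available juice and taste additives (ginger"). Under Task1.1, on cultivation and juice production: "The carrots will subsequently be transported to OF and NF, for production of both the carrot and the placebo juice". The section Product - carrot juice and placebo adds that taste is corrected so that the two juices cannot be told apart. It does not say what is added to the active juice.

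On screening, Scenario 1 says that after the colonoscopy "the endoscopist will consider the inclusion and exclusion criteria", before the patient is told about the study. The section Information collected from patient files and questionnaires lists among the file data "Quality and technical details of both colonoscopy, allergies, former colonoscopies and polypectomies". It says that patients with a polyp above 20 mm are invited "regardless of other information from the patient journal which we will not access at this timeline", and then: "Patient information will not be collected at the inclusion but will be accessed by research responsible", with entry into the database once the patient is already in the project. Common pathway has 8 litres of juice, a two-month supply, given out on inclusion. The Randomization paragraph allocates 50/50 within each centre.

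**The concern.** In a blinded two-arm trial the product is not known when eligibility is decided, so a participant has to be able to take either one. An allergy criterion that covers the main ingredient of one arm only does not meet that condition. Here the protocol itself names a non-carrot ingredient, ginger, in the placebo, and describes the placebo's base as a different juice. No listed exclusion covers an allergy to either.

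The order of steps adds to this. The protocol plans to obtain each patient's recorded allergies, but at a point where the information can no longer prevent the first hand-out. What is at stake is avoidable exposure of a participant to something that he or she is already known to react to.

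**Working it through.** The documents give no figure on this point, so there is none to reproduce. The check sets the sections side by side.

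1. **Criterion against product.** Exclusion 4 covers carrots. The stated placebo ingredients are commercial (in one place, artificial) juice and ginger. Exclusions 1 to 3 concern many small polyps, mental illness or expected poor compliance, and pregnancy. None of the four applies to a patient with a known ginger allergy, or with a known allergy to a component of the commercial juice. By the listed criteria that patient is eligible.

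2. **Chance of exposure.** With 50/50 allocation, a patient allergic to an ingredient found only in the placebo has probability 0.5 of receiving it. If k such patients are included, the expected number exposed is k × 0.5 = k/2. If the same ingredient is also in the active juice, all k are exposed. The protocol does not say which case holds, because the active juice's taste additives are unnamed. It gives no value for k.

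3. **Order of steps.** The journal is not consulted at invitation. At inclusion, the juice is handed out. After inclusion, the file is opened and its data are entered. The recorded allergy is therefore read after the patient has a two-month supply at home (8,000 ml at 100 ml a day is 80 daily portions). The text does not say how long after inclusion the file is read.

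4. **Consistency of the screening text.** Scenario 1 has the endoscopist go through the criteria before the offer. The data-collection section describes invitation on polyp size without the journal. Both can be true if the endoscopist asks the patient, but the protocol does not say so. The next section, Patient information from patient journals, lists the journal items without allergies, so it is not even consistent that the entry will be retrieved.

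5. **Placebo source.** Task1.1 sends carrots to the producers for both juices, and Time schedule mentions inactivation in connection with the placebo experiments. Design of the intervention and the risk section describe commercial juice. An allergy criterion cannot be matched to the products until this is settled.

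**The case against.** Much can be said against a broad version of this point, and part of it stands.

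- **Carrot allergy is screened.** The exclusion concerns a known allergy, which can be learned by asking, and Scenario 1 provides for a check before the offer. A reader might infer from the data-collection section that eligibility goes unchecked. The text does not support that: it limits access to the journal and does not waive the criteria. What remains for carrots is only a recorded allergy that the patient does not mention.
- **Scenario 2 does not repeat the check.** A reader might infer that those patients are not screened. But the exclusion list applies to all patients, and Patient recruitment, which introduces both scenarios, makes the offer conditional on the absence of contraindications. The silence is a drafting difference.
- **The contraindication clause might cover other allergies.** It could be read that way, but the term is undefined and nowhere tied to the ingredients of the juices. It does not close the gap.
- **Earlier use was uneventful.** Ethics reports that the juice and placebo were used in an earlier trial without side effects being seen. It gives no numbers and does not say whether anyone with a relevant allergy took part.
- **An informed patient may decline.** Patients get oral and written information and at least 48 hours to think. If that material lists the ingredients, a patient who knows of an allergy may stay out. The material is an attachment that is not at hand, so this can be neither counted nor dismissed.
- **Bias and unblinding.** A reader might infer that reactions and stops would gather in the placebo arm, distort the comparison of side effects and compliance, and reveal what the juice letters mean. That requires the additives to be in the placebo only. Since the active juice is also taste corrected with unstated additives, the documents do not establish it.

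**Conclusion.** The point holds in a narrow form. Exclusion 4 does not match the products as the protocol describes them, so a patient with a known allergy to a non-carrot ingredient meets no listed exclusion and can be randomised to a juice containing it. The planned reading of the allergy entry comes too late to prevent the first hand-out.

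This rests on the explicit descriptions of the placebo as commercial juice with ginger. If the placebo were instead made from carrots, as Task1.1 can be read, the existing exclusion would cover its base but still not its taste additives.

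The improvement is small and concerns participant safety. It has no bearing on the sample size or the primary analysis, and no effect on power, bias or blinding is shown. How many patients are affected cannot be derived from the documents, and any count would rest on a prevalence that they do not give. The point is still worth acting on, because the mismatch is in the protocol's own text and costs almost nothing to remove.

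**What to change.** 1. State the composition of both juices, and reconcile exclusion 4 with it so that the criterion covers known allergy to an ingredient of either product.
2. Move the already planned look-up of the allergy entry to after signed consent and before randomisation and the first hand-out, for both recruitment scenarios. This fits the section Data collection, management and analysis, which already places data collection after consent.
3. Reconcile Scenario 1 with Information collected from patient files and questionnaires on when eligibility is checked and when the file is opened. Align the list in Patient information from patient journals, which omits allergies.
4. Reconcile Task1.1, Design of the intervention and the risk section on what the placebo is made from, and check the mention of inactivation in Time schedule against the result.

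The cost is a wording amendment and a change in the order of one step. Very few patients would be lost.

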#### Sample size:

Patients seen at the one-year follow up after high risk polyps have 40 % chance of having new polyp/polyps at the colonoscopy. The difference in polyp number found between treatment and control in rats was 40%. The difference in large polyps was 80 % but this is based upon small numbers. The possible effect in humans is unknown. A difference of 10 % or 20 % would be of clinical interest. To test for a difference of 20 % would demand the enrolment of 1248 persons, which is not realistic.

The study is dimensioned to prove a significant difference in number of polyps after 3 years and a significant difference in the combined endpoint (number x size) after 1 year of treatment. The expected effect in number of adenomas in the active and the control arm is a > 20% reduction (corresponding to a 50% relative reduction).

- 1. The recurrence rate is estimated to 40%
- 2. The acceptance rate to participate is 55%.
- 3. The exclusion rate is 20%
- 4. The total drop-out rate is expected to be 20%.
- 5. The drop-out patients are estimated to an average 6 months participation.

We assume 80% power and a standard deviation of 5%. Using a two-sided X2-test, a total of 726 patients have to be invited with a minimum of 328 patients to complete the trial. Due to the expected variability of the factors above, we aim to include a total of 400 patients equally to either case or controls. Achieving this number of included patients will require approximately 1.000 possible candidates to be invited. The combined capacity of the included centers is 1.600 eligible patients per year. Therefore, we estimate that the enrollment can be completed within 12 months.

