# **Common pathway**

At the inclusion visit, a compliance diary/calendar will be handed out for registration of compliance and also a basic questionnaire. Patients will be given 2 months juice (8 liters) when included and will be appointed after 2 months to collect another 8 liters of juice in the department. Patients will be informed that they will receive a call after 1 month from each appointment, where their questions and concerns are answered. If the patients need to reschedule the appointment he/she can call at the number that will be written on the information paper or if he/she doesn't show up, the dedicated staff will contact them on the number they wrote in the questionnaire.

Regarding of the recruitment scenario (1 or 2), in order to follow the national guidelines, patients who have had a piecemeal resection will have an additional control colonoscopy at 3 months.

All patients will undergo a full colonoscopy at one year from the moment of the enrollement After the procedure, information about recurrence, the number of polyps, polyp size and characterization will be registered in the database. Polyp size will be measured with the aid of appropriate instruments, like biopsy forceps and slings.

After completing the study period of 1 year, all patients will enter the standard follow up program.

[figure not shown]
Full compliance is defined as consumption of > 75% of the juice delivered. However, because we do not know the minimal effective dose, all participants will be encouraged to continue the study even if they had drop-outs of juice consumption that lead to a < 75% compliance. In addition, participants with incomplete compliance will be registered and included in the study as a sub-group for separate analysis. But the project nurse will assess the patients every 2 months when they pick up the juice and if almost complete non-compliance is registered, the patient will be excluded from the study.

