**Randomization:** The study is designed as a double-blinded, randomized controlled study. The randomization is stratified by inclusion center, each having its own block of 50/50 distribution between active and placebo arm. Each unit will receive blocks of juice marked A and B for the active juice or either the placebo juice. The randomization key is generated in the RedCap randomizer. The juice producer holds the key for supplementary delivery to each participant center every 6 months. New shipments are delivered, marked with the same randomization letter.

When the last patient has taken the last dose, the code is broken and patient identity and information of active/placebo juice is combined in the database by an independent staff member.

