# Data retention, storage, destruction and publication

All data will be stored in the electronic database REDCap via OPEN on password-protected computers. All electronic data will be backed up and stored electronically in password secured computers. All paper data will be archived and stored in a locked cabinet in the Research Office of the Department of Surgery, OUH. Data retrieved from EPJ is transferred to the RedCap database directly. Data is stored securely in the RedCap database for 5 years (until 31 December 2028), after which will either be destroyed or transferred to the National Archives.

Additionally, we plan to publish the findings in a peer-reviewed journal. Participant anonymity and confidentiality will be preserved as only aggregated findings will be presented or reported. In case of data breach, the incident will be reported to Datatilsynet and the affected participants will be informed.

The Data Protection Regulation and the Data Protection Act are complied. The project is registered with the Data Protection Agency before the start of the project.

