# Time schedule:

The clinical studies:

Protocol for the Px7 trial will be finished before October 1'th 2023, including approval from the ethical committee and the data protection agency.

Database and electronic randomization algorithm will be ready before October 1'th 2023

Experiments with placebo juice ended before October 2023. For effective inactivation and taste adjustments.

Planting carrots will be ordered in March 2023 (done) and harvested in October 2023 and October 2024

Contract on juice production before July 2023 (done)

Questionnaires for patients will be finished before December 2023.

Inclusion of patients into the px7 trial will await the 2023 carrot harvest. It can be initiated November 2023. Inclusion will take 12 month, and observation until follow up colonoscopy will be ended January 2026.

Publications will be produced before January 2027.

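### The claim that the trial is sized for a difference in polyp number after 3 years is supported neither by the sizing inputs nor by the 1-year design

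*Protocol*

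**What the plan says.** The Sample size section gives the trial two targets at two times. For polyp number it states "The study is dimensioned to prove a significant difference in number of polyps after 3 years". For the other target it names "a significant difference in the combined endpoint (number x size) after 1 year of treatment".

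The operational sections describe a single year:

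- Design of the intervention: each arm drinks juice daily for 1 year, up to the follow-up colonoscopy.
- Inclusion criteria: "The patient is willing to accept the treatment and follow-up program for1 year".
- Outcome measures: the primary outcome is polyp number and size at the one-year colonoscopy. Neither the primary nor the secondary list has a 3-year item.
- Common pathway: "After completing the study period of 1 year, all patients will enter the standard follow up program".
- Patient inclusion: the last patient finishes at month 24.
- Randomization paragraph: "When the last patient has taken the last dose, the code is broken".
- Time schedule: observation ends in January 2026, and "Publications will be produced before January 2027".

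Two places look further ahead. The Abstract says that guidelines offer high-risk patients a colonoscopy after 1 and after 3 years. The section on information collected from patient files says "Data will be destroyed after publication of the results from the 3-year colonoscopy", or later if an extension to 5 years is applied for.

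**The concern.** A statement that a study is dimensioned to prove something is a confirmatory claim. It tells the reader that the sample size was derived for that comparison and that the design will deliver it. Here the comparison has no defined outcome, no scheduled assessment and no sizing input of its own.

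The time point for polyp number is also unclear. Sample size places number at 3 years, Outcome measures makes it part of the 1-year primary outcome, and the Aim section claims significance for a 40% difference in number without naming a time. A reader cannot tell from these three places when number is meant to be tested. A later 3-year result could be presented as the comparison the trial was sized for, although it was not.

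**Working it through.** **1. The sizing inputs.** All come from the Sample size section.

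- Recurrence 40%, stated for patients seen at the one-year follow-up.
- A reduction of 20 points, described as 50% relative, so 40% against 20%.
- Power 80%, two-sided chi-square test. Alpha is not stated; 0.05 is assumed here.
- Drop-out 20%, with drop-outs taking part for 6 months on average, which is attrition within the treatment year.
- At least 328 completers; 400 to be included.

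The plan's own figure: n per arm = [1.96·√(2·0.30·0.70) + 0.842·√(0.40·0.60 + 0.20·0.80)]² / 0.20² = (1.270 + 0.532)² / 0.04 ≈ 81.2. That rounds up to 82 per arm, or 164 in total. The stated 328 is 2 × 164, so it is not reproduced from the stated inputs. That is a separate matter. What counts here is that no input in the list refers to year 3.

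**2. The calendar.** Inclusion starts in November 2023 and takes 12 months, so it runs to November 2024.

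| Event | Derivation | Date |
|---|---|---|
| Last dose, code break | month 24, or the January 2026 end of observation | Nov 2025 to Jan 2026 |
| First 3-year colonoscopy | Nov 2023 + 36 months | Nov 2026 |
| Last 3-year colonoscopy | Nov 2024 + 36 months | Nov 2027 |
| Publications due | Time schedule | before Jan 2027 |
| End of data retention | data retention section | 31 Dec 2028 |

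If January 2026 is taken as the last 1-year visit, the last 3-year colonoscopy moves to January 2028.

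- From code break to first 3-year colonoscopy: 10 to 12 months. Every 3-year colonoscopy therefore follows the code break.
- For an individual patient the code break comes 1 to 2 years after enrolment.
- Share reaching 3 years by January 2027, under even accrual: 2/12 = 17%.
- Share of the 36 months spent on juice: 12/36 = 33%.

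**3. Who sets the 3-year visit.** The protocol's last scheduled procedure is the one-year colonoscopy. Afterwards patients follow standard care. The section on deviation from standard treatment gives that as 18 months for the full colonoscopy in Denmark since May 2023, and 1 to 3 years in Sweden. The timing of any later colonoscopy is outside the protocol's control.

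**4. What year 1 to 3 losses would do (illustration only).** Completers at year 1: 400 × 0.8 = 320. The documents give no later attrition, so 10% to 40% is assumed, leaving 288 to 192 patients. The 40% one-year rate is carried over to year 3, which is also an assumption. Power is for a comparison of proportions.

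| Rates compared | 288 patients | 192 patients |
|---|---|---|
| 40% v 20% | 0.96 | 0.86 |
| 40% v 24% | 0.83 | 0.66 |
| 40% v 32% | 0.29 | 0.21 |

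Loss of patients alone would not sink a 3-year test if the full 20-point difference persisted two years after the juice stopped. With a smaller difference it could. The protocol gives no basis for choosing among these rows, so the claim of being dimensioned for year 3 cannot be checked.

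**The case against.** The strongest reply is that 3-year data are foreseen and obtainable. The Abstract mentions a guideline colonoscopy at 3 years, the data section expects to publish its results, and retention to 31 December 2028 covers every 3-year date in the table. A comparison by randomised arm after treatment has stopped is also a legitimate question about a lasting effect. All of this stands. A reader might infer that the 3-year question cannot be answered at all, or that any such comparison is invalid; the documents do not support either.

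Other stronger readings also go too far:

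- **Blinding ends at 1 year.** The code is broken after the last patient's last dose, at about month 24. An independent staff member then links allocation to identity in the database. The protocol does not say that patients or routine endoscopists are told the arm. Knowledge of allocation at year 3 is a risk, not a stated fact.
- **Consent ends at 1 year.** The inclusion criterion concerns willingness to follow a 1-year programme. The consent form is not available for review, and the data section describes record access without a 1-year limit.
- **The 5-year extension contradicts the retention date.** It is conditional and would need its own application.
- **A null 1-year result would be deferred to year 3.** The primary outcome is fixed at the one-year colonoscopy, and nothing lets a later result replace it.

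None of this supplies a 3-year outcome, visit, rate, effect or attrition allowance. An analysis plan could define an analysis, but it could not turn one-year sizing inputs into 3-year ones.

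**Conclusion.** The point holds in a limited form. The Sample size section claims confirmatory sizing for polyp number at 3 years, and neither the sizing inputs nor the 1-year design supports it. Any 3-year comparison would come two years after the juice stops, after the code break, at times set by routine care, and for about 83% of patients (10/12) after the publication deadline.

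The dates assume that inclusion starts in November 2023, takes 12 months and is even. Slower accrual would push the 3-year dates later and not change the conclusion. The 1-year primary comparison is untouched. The defect is a claim the design does not back, not a flaw that defeats the trial.

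**What to change.** - In Sample size, delete the statement that the study is dimensioned for a difference in polyp number after 3 years. State that confirmatory conclusions, including those on number, rest on the 1-year colonoscopy.
- If 3-year data are kept, describe them as exploratory post-treatment follow-up by randomised arm, after the code break. State which lesions are counted; that definition is the sponsor's choice.
- Confirm that the consent covers collection of the later colonoscopy results.
- Reconcile Sample size, the section on information from patient files, and Time schedule, so that the 3-year results and the publication date agree.

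The cost is protocol wording and a less favourable stated claim. No change to sample size, treatment or the 1-year assessment is needed.
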